#### **Adverse Events of Clinical Interest**

The following are considered to be AEs of clinical interest:

- ALT or AST >3× ULN
- Severe or serious ISRs; ISRs that are associated with a recall phenomenon (reaction at the site of a prior injection with subsequent injections), or ISRs that lead to temporary dose interruption or permanent discontinuation of study drug.

An ISR is defined as a local reaction at or near the site of injection. "At or near" the injection site includes reactions at the injection site, adjacent to the injection site, or a reaction which may shift slightly away from the injection site due to gravity (eg, as may occur with swelling or hematoma). Reactions with onset and resolution within 4 hours of the injection (eg, transient pain/burning at injection site) do not meet the study definition of ISRs, unless immediate treatment is required. A systemic reaction which includes the injection site, eg, generalized urticaria, other distinct entities or conditions like lymphadenopathy that may be near the injection site is not considered an ISR.

For information on recording and reporting of AEs of clinical interest, see Section 6.5.5.2 and Section 6.5.5.3, respectively.

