#### **Recording Adverse Events**

The Investigator is responsible for recording non-serious AEs that are observed or reported by the patient after administration of the first dose of study drug regardless of their relationship to study drug through the EOS. Non-serious AEs will be followed until the EOS. Events occurring after signing of the ICF and before study drug administration will be captured as medical history (see Section 6.1), while AEs that occur after study drug administration, and baseline events that worsen after study drug administration, must be recorded as AEs.

The Investigator is responsible for recording SAEs that are observed or reported by the patient after the time when the informed consent is signed regardless of their relationship to study drug through the EOS. Serious AEs will be followed until satisfactory resolution, until baseline level is reached, or until the SAE is considered by the Investigator to be chronic or the patient is stable, as appropriate.

All AEs must be recorded in the source records for the clinical study center and in the eCRF for the patient, whether or not they are considered to be drug-related. Each AE must be described in detail: onset time and date, description of event, severity, relationship to study drug, action taken, and outcome (including time and date of resolution, if applicable).

For SAEs, record the event(s) in the eCRF and, as applicable, the SAE form.

For AEs that are considered AEs of clinical interest (Section 6.5.5.1), the supplemental AEs of Clinical Interest eCRF should be completed. Additional clinical and laboratory information may be collected. Refer to eCRF completion guidelines for details on reporting events in the supplemental AEs of Clinical Interest eCRF.

For all ISRs, the Investigator, or delegate, should submit an Injection Site Reaction Signs or Symptoms eCRF, recording additional information regarding each injection site reaction that is entered on the AE eCRF (eg, symptom(s), injection site location, follow-up actions taken, etc.).

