Listings of all deaths, SAEs, and AEs leading to treatment discontinuation will be provided.

Selected AE tabulations will include number of AEs and event rates per patient-year. In these summaries, multiple occurrences of the same AE in a patient will be counted multiple times for that patient.

AE summary tables (by SOC and PT) will be separately generated for each of the subgroups below:

- Sex (Male, Female)
- Race (White, Black, All other)
- Region (US, Europe)

AEs of Clinical Interest

The following AECI will be summarized by SOC and PT:

• Severe or serious injection site reactions (ISRs): AEs mapping to the HLT "Injection Site Reactions" using MedDRA dictionary.

A tabulation will also be generated to display the number of patients with at least 1 ISR, total number of doses (any dose split into multiple injections will be considered 1 dose in summary), total number of doses with ISRs, and the signs and symptoms reported due to ISRs. If there are multiple ISRs that occur in between 2 consecutive injections, then these events will be considered as 1 ISR and considered related to the earlier injection.

• ALT or AST >3xULN: AEs mapping to certain standardized MedDRA queries (SMQs) will be summarized by SOC and PT.

All AEs will be presented in patient data listings. AEs mapping to the SMQs as described above will also be listed.

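### The SAP's summary of adverse events of clinical interest departs from the protocol definition: recall and dose-interrupting injection site reactions get no count of their own, and the ALT/AST row is filled from unnamed coded queries

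*SAP*

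**What the plan says.** Protocol section 6.5.5.1 names two groups of adverse events of clinical interest (AECIs). The first is a laboratory threshold, "ALT or AST >3× ULN". The second is a set of ISRs: those that are severe or serious, "ISRs that are associated with a recall phenomenon", and "ISRs that lead to temporary dose interruption or permanent discontinuation of study drug". Recall means a reaction at an earlier injection site after a later injection. The recall and dosing limbs carry no severity condition, so a mild ISR qualifies if it recurs at an old site or holds up a dose. For every AECI, section 6.5.5.2 says that "the supplemental AEs of Clinical Interest eCRF should be completed", and section 6.5.5.3 requires the sponsor to be notified within 24 hours. A separate eCRF on signs and symptoms is completed for all ISRs.

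SAP section 5.11.1 has its own AECI paragraph. Its ISR item reads "Severe or serious injection site reactions (ISRs): AEs mapping to the HLT" for injection site reactions. Its liver item carries the label for ALT or AST above 3 times ULN, but the rule under that label is "AEs mapping to certain standardized MedDRA queries (SMQs) will be summarized by SOC and PT". The queries are not named there, and no laboratory value enters the rule.

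**The concern.** A reader of the study report will take a table headed with the protocol's AECI term to mean the protocol's events. As written, the SAP's ISR summary leaves out any mild or moderate, non-serious ISR that showed recall or affected dosing. The transaminase row can include a coded hepatic event in a patient who never passed 3 times ULN, and can leave out a patient who did if no selected term was reported.

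The content matters because protocol section 1.3 gives hepatic effects as the important potential risk and notes that ISRs have been observed. Section 3.6 says there is no safety review committee, so these descriptive tables carry much of the safety reading. Recall is also a pattern that a plain count of ISRs does not reveal.

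**Working it through.** No arithmetic bears on the size of the problem, because the documents give no expected rate for AECIs, ISRs or transaminase elevations. The check compares the texts.

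**Is it a version effect?** No. The AECI definition is the same in the original protocol and both amendments. SAP section 6 lists three changes from the protocol (the stratification mean, the Plasma Oxalate Analysis Set and the Safety Analysis Set). None concerns AECIs.

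**Where does each protocol trigger appear in the SAP?**

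| Protocol trigger | AECI summary (SAP 5.11.1) | Elsewhere in the SAP |
|---|---|---|
| ALT or AST above 3 × ULN | Label kept; rule is coded terms from unnamed queries | Laboratory bands from above 3 × ULN and a patient listing (5.11.2) |
| Severe or serious ISR | Yes, by MedDRA high level term | Any-ISR table |
| ISR with recall | No | Nothing that identifies recall |
| ISR interrupting dosing | No | One overall row for any AE leading to drug interruption; not ISR-specific |
| ISR ending dosing | No | SOC/PT table and listing of AEs leading to discontinuation |

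Of five triggers, one is summarised under its own definition, one under a different rule but captured elsewhere, and one is outside the summary but recoverable. The other two have no ISR-specific count: 5 − 1 − 1 − 1 = 2.

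**Can the any-ISR table fill the recall gap?** No. It counts patients with an ISR, doses with an ISR, and signs and symptoms, without a split by recall. The SAP also merges several ISRs falling between two consecutive injections into one, attributed to the earlier injection. Doses are given on Day 1, Month 3 and Month 9, so recall can arise after two of the three (3 − 1). Suppose that after the Month 3 dose a patient reacts at the new site and again at the Day 1 site. The rule turns these into a single ISR belonging to Month 3, and the recall reaction disappears from the count. The SAP does not say whether the rule also covers the period after Month 9, which no later injection closes.

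**Can interruption be read off another table?** Not for ISRs. Discontinuation has a breakdown by SOC and PT; interruption has only the single overall row.

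**What does the laboratory section give for the liver item?** It gives frequency and shift tables in bands of above 3 to 5, above 5 to 8, above 8 to 20 and above 20 times ULN, for ALT, AST and either. It also gives a listing of every patient above 3 times ULN. The total above the threshold is the sum of the four bands, provided each patient is placed once, by worst value; the SAP does not state this for the frequency table. It also leaves open whether central data alone or central plus local data are used.

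**A smaller difference.** The protocol's ISR definition excludes, unless immediate treatment is required, "Reactions with onset and resolution within 4 hours of the injection". The SAP's high level term rule does not repeat that exclusion.

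**The case against.** The strongest reply is that the protocol promises no AECI table. Its definition governs the supplemental eCRF and rapid notification. The safety analysis section (7.2.8) does not mention AECIs and leaves further summaries to the SAP. That stands: no analysis promised in the protocol is dropped. But the SAP chose to summarise AECIs under the protocol's term, and it neither applies the protocol's definition nor records the difference.

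Second, a row headed severe or serious ISRs counts what its label says. This also stands. The fault there is omission. It does not extend to the transaminase row, whose label and rule differ.

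Third, the hepatic threshold is applied to laboratory values in section 5.11.2, in more detail than the AECI definition asks, with bilirubin criteria and plots besides. This stands and removes most of the liver concern. What is left is the label on the query row and the single-placement and laboratory-source questions.

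Fourth, table shells are in a separate document that may name the queries, and the overall AE table is open to further rows. That is possible, and the queries' coverage cannot be judged without their names. The shells are not available here, so the point is confined to what the SAP states.

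Fifth, the protocol text does not show that the eCRF has a discrete field for recall. This is fair and affects the cost of the fix.

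**Conclusion.** The SAP does not apply the protocol's AECI definition and does not say so. The real gaps are two kinds of ISR (recall and temporary interruption) with no count of their own, a merging rule that can hide recall, and a query-based row that need not match its label. Measured against the protocol definition, the ISR summary will undercount whenever a mild or moderate, non-serious ISR shows recall or affects dosing. By how much, and whether unevenly between arms, cannot be calculated from the documents.

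A reader might infer three stronger things. The documents support none of them.

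- That the safety tables in general give wrong counts by arm. The shortfall is against one definition in one summary; all AEs are still listed by patient.
- That the hepatic signal is compromised. Laboratory tables and a listing already capture it.
- That ISRs ending treatment are lost. They appear by preferred term in the discontinuation table, and in a listing.

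Safety is descriptive, so no test is affected; the primary efficacy analysis and sample size are untouched. This is a minor but worthwhile correction. It assumes that the shells do not already supply the missing rows and query names.

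**What to change.** In SAP section 5.11.1, define AECIs as in protocol section 6.5.5.1 and identify them from the AECI and ISR eCRFs. Then:

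- Show one ISR row each for severe or serious, recall, and interruption or discontinuation, by arm. Identify recall before the merging rule is applied.
- Take the row for ALT or AST above 3 times ULN from laboratory values, counting each patient once by worst value, and state whether local results are included.
- Keep the query table, relabelled as a supportive hepatic AE summary with the SMQs named.

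If the sponsor prefers the narrower set, the least that is needed is an entry in SAP section 6 giving the difference and the reason, and a corrected label on the query row.

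The cost is some SAP wording and a few rows for events that sites must already flag. Recall cases may need individual review if the eCRF has no discrete field for them.

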5.11.2. Laboratory Data

Clinical laboratory values will be expressed in SI units. Missing laboratory data will not be imputed.

For each continuous clinical laboratory parameter (hematology, serum chemistry, and liver function tests), descriptive statistics will be presented for the actual values, change from baseline, and percent change from baseline by visit. These by-visit tables will use central laboratory data only. eGFR will not be reported in this section, as this is summarized in the efficacy section (Section 5.7.3.3). For any local collections of LFTs and others, these will be included in a separate data listing.

Select clinical laboratory parameters may be graded according to the National Cancer Institute CTCAE Version 5.0 or above. Shift summary from baseline CTCAE grade to maximum (worst) post-baseline grade will be presented for all graded parameters with directionality specified (e.g., hyper or hypo). To determine the worst post-baseline value, all scheduled and unscheduled test results will be used. For hematology and serum chemistry, frequency tables of potentially clinically significant abnormalities will be provided. For select shift and summary tables such as LFT summaries, one or both of the following approaches may be utilized: 1) Only central laboratory data will be included; 2) Both central and local laboratory data will be included.

All laboratory data (both central and local) will be provided in data listings. Out-of-range laboratory results will be presented in a separate listing with proper flags. Local laboratory data, if available, will also be flagged.

Liver Function Tests

A frequency table and a shift table will be produced to summarize the number and percentage of patients in each of the below categories at any post-baseline time point.

- ALT >1 & ≤3, >3 & ≤5, >5 & ≤8, >8 & ≤20, >20×ULN,
- AST >1 & ≤3, >3 & ≤5, >5 & ≤8, >8 & ≤20, >20×ULN,
- ALT or AST >1 & ≤3, >3 & ≤5, >5 & ≤8, >8 & ≤20, >20×ULN,
- ALP > $1.5 \times ULN$,
- Total Bilirubin >1.5 & ≤2, >2 & ≤3, >3 & ≤5 and >5×ULN,
- Total Bilirubin $> 2 \times ULN$ concurrent with ALT or AST $> 3 \times ULN$

In separate figures, the peak total bilirubin (as multiple of ULN) at any time post-baseline will be plotted against the peak ALT level and (peak AST and the peak AST or ALT levels) at any time post-baseline.

A listing for all patients with abnormal liver function tests, defined as an ALT $>3\times$ ULN, AST $>3\times$ ULN, or total bilirubin $>2\times$ ULN at any time point, will also be provided.

5.11.3. Vital Signs and Physical Examination

For vital signs and body weight and height, descriptive statistics for actual values and change from baseline by visit will be provided for each variable. Vital sign measurements will be presented for each patient in a data listing, with abnormal vital signs flagged.

5.12. Interim Analysis

No formal interim analysis is planned for this study.

5.13. Other Analyses

Additional data are collected to characterize the impact of the COVID-19 pandemic on general study conduct and disposition, and subsequently, additional analyses and summaries will be provided in acknowledgement of multiple regulatory guidance (including FDA Guidance on Conduct of Clinical Trials of Medical Products during COVID-19 Pandemic: Guidance for Industry, Investigators, and Institutional Review Boards, US Food and Drug Administration, 2020; Guidance on the Management of Clinical Trials during the COVID-19 (Coronavirus) Pandemic, European Medicines Agency, 2020; Points to consider on implications of Coronavirus disease (COVID-19) on methodological aspects of ongoing clinical trials, European Medicines Agency, 2020; Statistical Considerations for Clinical Trials During the COVID-19 Public Health Emergency, US Food and Drug Administration, 2020).

5.13.1. General Impact

Patients who discontinue treatment or stop study participation due to COVID-19 will be included in patient disposition summaries.

Impact on study participation due to COVID-19, including missing visits, visit location changes, study drug dosing changes and missing doses, will be summarized descriptively overall and by visit on the patient level, and overall on the event level. Patient- and event-level summaries of the impact on study participation due to COVID-19 may also be generated by site and/or region.

Impact on study participation due to COVID-19 will be presented in data listings at patient and visit level.

5.13.2. Impact on Efficacy

COVID-19 pandemic impacted efficacy analyses are not carried out for the primary analysis since efficacy assessments (e.g., blood and urine samples for PD) missed due to COVID-19 pandemic are expected to be minimal.

Given the measures specified in the protocol designed to ensure data integrity, analyses excluding patients with COVID-19 related protocol deviations will not be prespecified, but may be considered post hoc, if warranted.

5.13.3. Impact on Adverse Events

An overall summary of AEs mapping to a COVID-19 custom query will be presented. AEs mapping to the COVID-19 custom query will be summarized by HLT and PT. Due to the evolving nature of COVID-19-related MedDRA terminology, the COVID-19 custom query will be based on the latest information available at the specified analysis timepoint.

AEs mapping to the COVID-19 custom query will also be presented in a data listing.

6. CHANGES FROM PLANNED ANALYSES

Below is a summary of changes/clarification from the protocol

SAP Original

Section of the SAP	Summary of change from protocol	Rationale
Section 2.4 and Section 4.5	Added the first 2 valid 24-hour urine collections to the calculation of the mean baseline urinary oxalate level stratification factor.	The addition of the first 2 valid 24-hr urine collections to the stratification mean baseline urinary oxalate improves clarity.
Section 3 and Section 5.8	Plasma Oxalate Analysis Set is added for the analysis of the plasma oxalate endpoint.	The LLOQ of the plasma oxalate assay is $5.55 \mu mol/L$. Due to the inability of quantify oxalate level below LLOQ by the assay, patients with baseline plasma oxalate level measured near to or at LLOQ are excluded from the analysis to ensure the meaningful reduction can be evaluated for the study population.
Section 3	Removed "randomized" from the Safety Analysis Set definition.	"Randomized" was erroneously entered in the protocol.

7. APPENDICES

7.1. Protocol Schedule of Assessments

		15 Month Double-Blind Treatment Period ^a										
	Screening	Primary Analysis Period Primary Analysis Period Period								nent sion od	Safety	
Study Visit			Baseline	M2	M3	M4	SM	M6	EOT M9	M12	EOS/ ET M15	Follow-up (Patients who D/C Treatment Early)
Study Day (±Visit Window)	Notes	-60 to -1	Day 1	57 (±7)	85 (±14)	113 (±7)	141 (±7)	169 (±14)	253 (±28)	309 (主7)	421 (±28)	3 and 6 months post last dose (±28)
Informed consent	Section 6.1	X										
Assign patient identification number	Section 3.4	х										
Demographics	Section 6.1	Х										194
Blood for DNA analysis	Unless tested previously, see Section 6.1.1	х										
Full physical examination	Section 6.5.3	X									X	
Follicle-stimulating hormone	To confirm post-menopausal status if applicable; Section 6.5.4.2	х										
Serum pregnancy test (for WOCBP)	See Section 6.5.4.2	X										

		15 Month Double-Blind Treatment Period ^a											
		Screening	Treatn Primary Analysis Period Perio								ient ion od Safety		
Study Visit			Baseline	M2	M 3	M4	MS	M6	EOT M9	M12	EOS/ ET M15	Follow-up (Patients who D/C Treatment Early)	
Study Day (±Visit Window)	Notes	-60 to -1	Day 1	57 (±7)	85 (±14)	113 (±7)	141 (±7)	169 (±14)	253 (±28)	309 (±7)	421 (±28)	3 and 6 months post last dose (±28)	
2 separate 24-hour urine collections	2 valid screening collections (see Section 6.2.1.1); a third collection may be required (see Section 6.2.1.1) Collect within 14 days prior to dosing (M9) or visit (M15); repeat if invalid. See Table 4	Х							x		х		
Inclusion/exclusion criteria	Section 4.1; Section 4.2	X	Xb										
Medical history	Section 6.1	X	X										
Height	Section 6.5.2	X	X								X	×	
Vital signs	Section 6.5.1	X	X		Х				Х		X	Х	
Body weight	Section 6.5.2	X	X		Х				Х		X	Х	
eDiary	Diet compliance check and 24-hour urine collection; Section 5.6.3	х			x	x	x	x	x		x		

		15 Month Double-Blind Treatment Period ^a										
		Screening	Primary Analysis Period Primary Period Per								nent sion od	Safety
Study Visit			Baseline	M2	EM3	M4	M5	M6	EOT M9	M12	EOS/ ET M15	Follow-up (Patients who D/C Treatment Early)
Study Day (±Visit Window)	Notes	-60 to -1	Day 1	57 (±7)	85 (±14)	113 (±7)	141 (±7)	169 (±14)	253 (±28)	309 (±7)	421 (±28)	3 and 6 months post last dose (±28)
Single 24-hour urine collection	Collect within 14 days prior to dosing (M3) or visit (M4, M5, M6); repeat if invalid. See Table 4				X	X	x	X				
Blood sample for PD analyses	Section 6.3	х	Х		х			x	x		х	
Blood for exploratory analyses	Section 6.6	х	х		x			x	x		х	
Spot urine sample for PD and exploratory analyses	Single void collections for PD and exploratory analyses should be collected as a first morning void when possible; Section 6.3	Xc	Xc	x	Xc	x	x	Xc	Xc	x	Xc	x
Clinical laboratory assessments	Section 6.5.4	Х	х		x			x	x		х	Х
Antidrug antibody sample	Section 6.5.4.1		Х		X			Х	Х		X	Х

			15 Month Double-Blind Treatment Period ^a									
		Screening	Primary Analysis Period Ex F							reatn Extens Perio	ient sion od	Safety
Study Visit			Baseline	M2	M3	M4	MS	M6	EOT M9	M12	EOS/ ET M15	Follow-up (Patients who D/C Treatment Early)
Study Day (±Visit Window)	Notes	-60 to -1	Day 1	57 (±7)	85 (±14)	113 (±7)	141 (±7)	169 (±14)	253 (±28)	309 (±7)	421 (±28)	3 and 6 months post last dose (±28)
Urine pregnancy test (for WOCBP) ^d	May be performed more frequently where required per local requirements, or if pregnancy is suspected. See Section 6.5.4.2		х		x				x			
Symptom-directed physical examination	Section 6.5.3		X		x				x			X
Exploratory DNA sample (optional)	Section 6.6		х									
BPI-Short Form (Question 3 only)	Pain assessment, collected in an eDiary; Section 6.7.1	х	х	X Continuous (at the time of a clinical kidney stone event)								
WISQOL	Collected in an eDiary; Section 6.7.2		X Continuous (at the conclusion of a clinical kidney stone event)								ne event)	
Prior and concomitant medications	Section 5.4					Cont	inuou	IS				
Clinical kidney stone events	Section 6.2.2					Cont	inuou	IS				

		15 Month Double-Blind Treatment Period ^a										
	Screening	Primary Analysis Period Period									Safety	
Study Visit			Baseline	M2	£M	M4	MS	M6	EOT M9	M12	EOS/ ET M15	Follow-up (Patients who D/C Treatment Early)
Study Day (±Visit Window)	Notes	-60 to -1	Day 1	57 (±7)	85 (±14)	113 (±7)	141 (±7)	169 (±14)	253 (±28)	309 (±7)	421 (±28)	3 and 6 months post last dose (±28)
Review/record adverse events	Section 6.5.5		Continuous									
Healthcare utilization	Section 6.8					Cont	inuou	IS				
Randomization	Window: 1 business day prior to Day 1 for study drug preparation		х									
Study drug administration	Section 5.2.2		X		X				Х			
Blood samples for PK analyses	Table 2; Section 6.4		X									
Low-dose kidney-protocol CT scan ^e	Section 6.2.2.2		X (-3 days window)								X	

Abbreviations: BPI=Brief Pain Inventory; CT=computed tomography; D/C=discontinue; DNA=deoxyribonucleic acid; ET=early termination; EOS=end of study; EOT=end of treatment; M=month; PD=pharmacodynamic; PK=pharmacokinetic;

WOCBP=women of child-bearing potential

Notes:

[•] When scheduled at the same time points, assessments of vital signs should be performed before physical examinations and blood sample collections, where feasible.

- Patients who discontinue study drug dosing for any reason will be encouraged to remain on the study to complete the remaining assessments so that their experience is captured in the final analyses (refer to Section 4.3.1).
- White columns indicate visits to the clinical study center; gray-shaded columns indicate study visits that may be conducted by a home healthcare professional, where applicable country and local regulations and infrastructure allow (at the discretion and with oversight of the Investigator, based on safety and tolerability), provided (for dosing visits) that the patient has tolerated a dose of lumasiran administered in the clinic. If a visit is conducted offsite, a body system assessment may be performed in lieu of a symptom-directed physical examination.
- In situations where a study visit is unable to be completed (either at the site or offsite by a healthcare professional), the Investigator (or delegate) will verbally contact the patient within the study visit window to assess concomitant medications, kidney stone events, and adverse events. Footnotes:

^a All assessments are required to be performed prior to dosing at dosing visits, except for the CT scan and PK sample collection.

- ^b Inclusion/exclusion criteria should be verified prior to randomization. Laboratory assessments conducted to confirm study eligibility will not be repeated unless the time between screening and randomization exceeds 4 weeks.
- ^c Samples for exploratory analysis will only be collected at these visits and will be aliquoted from the samples provided for PD analysis.
- ^d Pregnancy test results must be known prior to dosing, if applicable.
- ^e May be performed after dosing, if required.

